### 7.1.4. Suspected unexpected serious adverse reaction (SUSAR)

A SUSAR is a serious adverse reaction of which nature or severity is not consistent with the applicable product information (e.g., Investigator's Brochure (IB) for an unapproved investigational product or package insert/summary of product characteristics for an approved product)

## 7.2. Reporting

#### 7.2.1. Adverse event

All AEs occurring during the trial that are observed by the Investigator or reported by the subject, will be recorded by the study personnel on the eCRF, whether or not attributed to trial medication. The following information will be recorded: description, date of onset and end date, severity, assessment of relatedness to trial medication and action taken. Follow-up information should be provided as necessary.

It will be left to the Investigator's clinical judgment to decide whether or not an AE is of sufficient severity to require the participant's removal from treatment. A subject may also voluntarily withdraw from treatment due to what he or she perceives as an intolerable AE. If either of these occurs, the participant must undergo an end of trial assessment and be given appropriate care under medical supervision until symptoms cease, or the condition becomes stable.

### 7.2.2. Adverse drug reaction

AEs considered related to the trial medication as judged by a medically qualified investigator or the Sponsor will be followed either until resolution, or the event is considered stable.

#### 7.2.3. Serious adverse event

All SAEs irrespective of relationship to study treatment (other than those defined in the protocol as not requiring reporting) must be reported on the SAE Reporting Form. The completed SAE Report Form should be sent via e-mail, within 24 hours from the Investigator's knowledge of the event, to the Safety Monitor at Pharm Assist Sweden AB, [contact].

### Deaths and Life-threatening SAEs should be immediately reported to

[contact].

If a verification of receipt has not been received within one working day, the SAE Report Form should be sent again.

Any SAE occurring after study completion and that is assessed by the Investigator as related to study treatment, should be reported to the Sponsor regardless of the length of time that has passed since study completion.

The SAE Report Form should be filled out as completely as possible at the time of the initial report. As a minimum, the initial SAE Report Form should contain the following information:

- Subject identification (subject identification code)
- Study identification
- Treatment specification
- Diagnosis or symptoms
- Time specification for the SAE
- Causality assessment
- Reporter identification

Any follow-up information received on SAEs should be forwarded within 1 (one) business day of its receipt. If the follow-up information changes the Investigator's assessment of causality, this should also be noted on the follow-up SAE Report Form.

Evaluation of relationship between the treatment and the SAE is to be made both by the Investigator and by the Sponsors's Medical Expert. If any of the parties decides that the SAE is related to the study product, the reaction is defined as a SUSAR and must be reported to the EudraVigilance database by Safety Monitor at Pharm Assist.

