### Causality

The investigator is responsible for determining whether there is a causal relationship between an AE and the use of a medicinal product.

All AEs are categorized either as unrelated, possibly related or related, as defined below:

- **Unrelated**: the AE is not reasonable in relation to the use of the medicinal product, or another cause can itself explain the occurrence of the event.
- **Possibly related**: the AE may be explained by the medicinal product and the onset is reasonable in relation to the use of the medicinal product, however there is insufficient information to determine the likelihood of this possibility.

• **Related**: the AE is most likely explained by the medicinal product and the onset is reasonable in relation to the use of the medicinal product.

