## 7.1.2. Adverse drug reaction (ADR)

An ADR is a noxious and unintended response to a medicinal product related to any dose administrated. The phrase responses to a medicinal product means that a causal relationship between a medicinal product and an adverse event is at least a reasonable possibility, i.e. the relationship cannot be ruled out.

The definition covers also medication errors and uses outside what is foreseen in the protocol, including overdose, misuse and abuse of the product.

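### Section 7.2.3 makes every SAE judged related a SUSAR, dropping the expectedness criterion of 7.1.4, and leaves unclear whether possibly related events count

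*Protocol*

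**What the plan says.** Section 7.1.1 (Causality) sets up a three-level scale: "All AEs are categorized either as unrelated, possibly related or related, as defined below". The top grade, *related*, applies when "the AE is most likely explained by the medicinal product". The middle grade, *possibly related*, applies when "the AE may be explained by the medicinal product and the onset is reasonable in relation to the use of the medicinal product", but too little is known to say how likely that is.

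Section 7.1.2 places the threshold for a drug reaction where a causal link is "at least a reasonable possibility, i.e. the relationship cannot be ruled out". Section 7.1.4 then adds expectedness: "A SUSAR is a serious adverse reaction of which nature or severity is not consistent with the applicable product information". As examples of product information it gives the Investigator's Brochure for an unapproved product and the package insert or summary of product characteristics for an approved one.

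Section 7.2.3 gives the rule that staff act on. Causality is assessed by both the investigator and the sponsor's medical expert, and "If any of the parties decides that the SAE is related to the study product, the reaction is defined as a SUSAR", with mandatory entry in EudraVigilance. Section 7.2.4 requires that all SUSARs be reported, within 7 calendar days if fatal or life-threatening and within 15 otherwise. Section 7.2.2, on adverse drug reactions, requires follow-up of "AEs considered related to the trial medication as judged by a medically qualified investigator or the Sponsor".

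**The concern.** The protocol holds two definitions of a SUSAR. The one in 7.1.4 needs a serious reaction that is also unexpected. The one in 7.2.3 needs only a judgement of relatedness, and it is the one attached to an action. Someone following 7.2.3 as written would send an expected serious reaction to EudraVigilance labelled as unexpected.

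Such reactions can exist here. Section 1.4 says Infudopa is not thought to cause systemic reactions beyond those already described for levodopa/carbidopa products and summarised in the Duodopa product information.

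The second worry is the word *related*. It names one of three defined grades, and 7.2.3 does not say whether the middle grade also triggers the rule. A reader who applies the defined terms strictly could leave a possibly related SAE out of the SUSAR step. That matters because the 7- and 15-day clocks in 7.2.4 run only once an event has been recognised as a SUSAR.

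**Working it through.** No sample size, power or event figure bears on this point, so the check sets the rules side by side.

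**Step 1. The protocol's own definition.** Combine 7.1.2 and 7.1.4. A serious event is a reaction if a causal link cannot be ruled out. Both *possibly related* and *related* in 7.1.1 meet that threshold. The reaction is a SUSAR only if it is also inconsistent with the product information.

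**Step 2. The operative rule.** Section 7.2.3 can be read in two ways: *related* as the defined top grade of 7.1.1, or *related* as a general word for any reasonable link.

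| SAE graded | Against product information | 7.1.2 with 7.1.4 | 7.2.3, defined grade | 7.2.3, general sense |
|---|---|---|---|---|
| Related | Unexpected | SUSAR | SUSAR | SUSAR |
| Related | Expected | Not a SUSAR | SUSAR | SUSAR |
| Possibly related | Unexpected | SUSAR | Not triggered | SUSAR |
| Possibly related | Expected | Not a SUSAR | Not triggered | SUSAR |
| Unrelated | Either | Not a SUSAR | Not triggered | Not triggered |

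The rows are kinds of event, not frequencies, so counting them does not measure the size of the problem.

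**Step 3. What holds on both readings.** The related, expected row disagrees with the definition in both 7.2.3 columns. On the general reading the possibly related, expected row disagrees as well. Neither reading of 7.2.3 reproduces 7.1.4.

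**Step 4. What depends on the reading.** The possibly related, unexpected row disagrees only if *related* means the defined grade. Even then, 7.2.3 says what happens if an event is judged related. It does not say that nothing else can be a SUSAR. Such an event is still a SUSAR under 7.1.2 and 7.1.4, and 7.2.4 requires every SUSAR to be reported.

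**Step 5. Whether another section repairs 7.2.3.**
- 7.2.3 assigns causality to two parties but expectedness to nobody. Its minimum content for the initial SAE form includes causality and no expectedness item.
- 7.2.4 starts from SUSARs already identified and contains no step to identify them.
- 11.1 keeps the unexpected condition for notifying the ethics committee, so that stream and the EudraVigilance stream use different criteria for the same event.

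The omission therefore stands.

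**The case against.** The strongest reply is that the certain defect errs on the cautious side. Reporting an expected reaction as a SUSAR costs administration and hides no risk. Every SAE goes to the Safety Monitor within 24 hours whatever its cause (7.2.3) and enters a safety database (7.2.5), so a possibly related SAE still reaches the role that files SUSARs. This stands, and it limits the seriousness. It does not remove the contradiction between 7.2.3 and 7.1.4.

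A reader might infer that expedited reporting is wrong in both directions, with unexpected, possibly related SAEs going unreported. The protocol does not establish that. Section 7.2.2 uses *related* without a grade label under the heading for adverse drug reactions, which 7.1.2 defines broadly, so a general sense is open. The trigger in 7.2.3 is not exclusive, and 7.2.4 still applies. On the other side, 7.1.1 names both degrees of relation when it defines infusion and catheter site reactions, so the protocol can be explicit when it means both. The result is an ambiguity with some risk, not a proven error.

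Three further inferences also lack support:
- **A wrong SUSAR count for the annual report or the interim Board.** Section 7.2.5 has the report summarise SAEs, and 8.4 gives the Board adverse events, dermal findings and PK data. Neither mentions a SUSAR count.
- **Section 5.2 as the source for judging expectedness.** It cites the reference safety information in connection with Duodopa administration.
- **A prediction that local reactions to the new s.c. buffer would be graded possibly related.** Nothing in the protocol says how they would be graded.

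**Conclusion.** The point holds in two parts of unequal strength. It is certain that 7.2.3 omits the expectedness criterion of 7.1.4, so any expected SAE judged related by either party would be misclassified as a SUSAR. This rests only on the two texts and does not depend on how *related* is read. It is unclear whether *possibly related* is inside the 7.2.3 trigger. The risk of missing an unexpected SAE with that grade arises only on the defined-grade reading, and only if staff stop at 7.2.3 without applying 7.1.2, 7.1.4 and 7.2.4.

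The frequency cannot be estimated, because the protocol gives no rate of serious reactions. No endpoint, estimate or sample size is affected. This is an internal inconsistency in an operative safety-reporting rule. It should be corrected because the rule carries regulatory clocks and the correction is simple.

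**What to change.** Reword the SUSAR sentence in 7.2.3 as a sequence:

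1. If the investigator or the sponsor's medical expert assesses the SAE as related or possibly related, it is a serious adverse reaction.
2. The sponsor then assesses expectedness against the applicable product information described in 7.1.4, with the document for each product named.
3. Only an unexpected serious adverse reaction is a SUSAR, reported under 7.2.4.

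Use *related or possibly related* in 7.2.2, and in the 7.2.3 rule for SAEs that occur after study completion. Adjust the SAE form instruction to match.

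The cost is one paragraph of protocol wording, two small wording changes and the form instruction. Patients, timeline and analysis are unaffected.

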### 7.2.4. Suspected unexpected serious adverse reaction

All SUSARs will be reported by Safety Monitor at Pharm Assist to the relevant Competent Authority and to EudraVigilance data base as applicable. For fatal and life-threatening SUSARs, this will be done no later than 7 calendar days after the Sponsor or delegate is first aware of the reaction. Any additional relevant information will be reported within 8 calendar days of the initial report. All other SUSARs will be reported within 15 calendar days.

### 7.2.5. Annual safety report

A safety report will be completed by Safety Monitor at Pharm Assist once a year and sent to the relevant Competent Authority and the Ethics Committee. The document will define the time period reported and summarize all occurred serious medical events (SAEs). The safety report should also always include a summary assessment of the safety of subjects that are still included in the trial and whether the benefit-risk assessment changed since the study was approved.

The Safety Monitor will establish and maintain a safety database, covering all SAEs in the study.

## 7.3. Procedures in case of pregnancy

Females of child-bearing potential are not allowed to be included in this study unless they use highly effective contraceptive measures. Contraceptive measures must be maintained during treatment and during the first menstrual cycle after relevant systemic exposure, which for the sake of this study is defined as the first 24h after cessation of treatment with Infudopa. The following contraceptive methods are considered highly effective: combined estrogen-progesterone hormonal contraceptives (oral, vaginal or transdermal), progesterone only hormonal contraceptives (oral, injected or implanted), intrauterine device with or without hormone releasing properties, bilateral tubal occlusion, vasectomized partner or sexual abstinence. Male subjects must refrain from fathering a child, including sperm donation, during the study and 3 months following the last dose. If the Investigator receives information that a pregnancy has occurred during the study (including pregnancy in the partner of a male subject) despite these restrictions, Safety Monitor at Pharm Assist should be informed and a specific Pregnancy Report Form completed.

### 7.3.1. Maternal exposure

If a subject becomes pregnant during the course of the study, investigational product should be discontinued immediately.

Pregnancy itself is not regarded as an adverse event unless there is a suspicion that the investigational product under study may have interfered with the effectiveness of a contraceptive medication. Congenital abnormalities/birth defects and spontaneous miscarriages should be reported and handled as SAEs. Elective abortions without complications should not be handled as AEs. The outcome of all pregnancies (spontaneous miscarriage, elective termination, ectopic pregnancy, normal birth or congenital abnormality) should be followed up and documented even if the subject was discontinued from the study.

If any pregnancy occurs in the course of the study, then the Investigator or other site personnel informs Safety Monitor at Pharm Assist within 1 day ie, immediately but no later than 24 hours when he or she becomes aware of it.

The same timelines apply when outcome information is available.

### 7.3.2. Paternal exposure

Male subjects should refrain from fathering a child or donating sperm during the study and for 3 months following the last dose. If a subject's partner becomes pregnant during the course of the study, investigational product should be discontinued immediately.

Pregnancy of the subject's partners is not considered to be an adverse event. However, the outcome of all pregnancies (spontaneous miscarriage, elective termination, ectopic pregnancy, normal birth or congenital abnormality) should, if possible, be followed up and documented. To capture information about a pregnancy from the partner of a male subject, the male subject's partner consent must be obtained to collect information related to the pregnancy and outcome; the male subject should not be asked to provide this information. A consent form specific to this situation must be used. The outcome of any conception occurring from the date of the first dose until 3 months after the last dose should be followed up and documented.

If any pregnancy occurs in the course of the study, then the Investigator or other site personnel informs Safety Monitor at Pharm Assist within 1 day, ie, immediately but no later than 24 hours of when he or she becomes aware of it.

The same timelines apply when outcome information is available.

# 8. STATISTICS

## 8.1. Sample size calculation

Sample size determinations are based on the primary pharmacokinetic variable from a similar study (Nyholm et al, 2013) regarding 16-hour intestinal infusion of Dudopa in advanced Parkinson's disease patients. Data from the 5 interim analysis patients are also used. A standard t-test model with continuity correction has been used (Microsoft Excel program, Pharm Assist Sweden AB). Z-alpha level was 1.96 and Z-beta level was 0.84 for equivalence testing of 90% CI of 0.80 to 1.25, and Z-alpha level was 1.65 and Z-beta level was 0.84 for non-inferiority testing of 90% CI of 0.80 to 1.25.

The test suggests that 14 subjects are appropriate for the test of dose-normalized AUC 0 to infinity of levodopa. This number of subjects is valid both based on the Nyholm et al. 2013 data for LCIG (COV 24.5%), and the data in the interim study (COV 17.0% allowing as a safety margin for a 40% higher COV, 23.8%, giving n=14).

For the non-inferiority test of intersubject coefficient of variation (COV) the sample size estimation suggests 18 subjects to be included.

Based both on the levodopa dose-adjusted AUC 0 to infinity and the intersubject COV it is planned that 22 subjects will be recruited to the study, also allowing for 4 drop-outs.

Clinical Study Protocol	Study code:	IPO-001
	Version No:	5.1
	Date:	26 MARCH 2019

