## 8.2. Statistical analysis

Statistical assessments of dosage normalized levodopa AUC0-inf, AUC0-last, AUC0-16, AUC0-2, AUC2-16, and AUC8-16 by analysis of variance (ANOVA) will be made on the logarithmic values, with back-transformation to nominal values of point estimates and confidence interval (CI). These variables will also be tested with dosage un-normalized values. The terms to be used in the ANOVA model will be sequence, patient within sequence, period, and formulation (i.v. or s.c. Infudopa and Duodopa; test and reference, respectively).

The statistical method for testing relative dosage normalized levodopa bioavailability will be based on the 90% CI for the ratio of the population means (test/reference). These statistical tests will also be done with dosage un-normalized values. The acceptance range for AUC ratio of the 90% CI for levodopa will be 0.80 to 1.25. These tests will be performed for Treatment 1 (i.v.) and Treatment 2 (s.c.) vs. Treatment 3 (Duodopa; reference) comparison, and for Treatment 1 (i.v. reference) vs. Treatment 2 (s.c.).

For each individual will be calculated the COV (coefficient of variation or % standard deviation; SD) for plasma concentration between 2 and 16 h by dividing the SD for each individual curve with the mean value of plasma concentration between 2 and 16 h. The mean value of plasma concentration will be calculated for each curve as AUC2-16/14. Basic statistics for the COV will then be calculated per treatment group. The one-sided 90% CI of the intersubject COV will be calculated for Treatment 1 (i.v.) and Treatment 2 (s.c.) vs. Treatment 3 (Duodopa; reference) comparison, and for Treatment 1 (i.v. reference) vs. Treatment 2 (s.c.). It will also be tested with paired t-tests if there are significant differences in intersubject COV between treatments (i.v. vs. Duodopa, s.c. vs. i.v., and s.c. vs. Duodopa).

The level of significance will be p=0.05.

Safety will be summarized with the standard set of AE summary tables, and descriptive summary statistics of vital signs by visit and change from baseline.

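### The n=14 for AUC equivalence comes from a difference-test formula with no stated COV type or true ratio, so the power of the planned 90% CI test is not established

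*Protocol*

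**What the plan says.** Section 8.1 names its method in one sentence: "A standard t-test model with continuity correction has been used". For the AUC comparison it gives "Z-alpha level was 1.96 and Z-beta level was 0.84 for equivalence testing of 90% CI of 0.80 to 1.25". Two variability figures lead to the same sample size for dose-normalised AUC0-inf. One is a COV of 24.5% for LCIG from a cited study of 16-hour intestinal infusion. The other is the interim figure, "COV 17.0% allowing as a safety margin for a 40% higher COV, 23.8%, giving n=14". The section does not say whether these COVs are between-subject, within-subject or of the paired difference, and it gives no assumed true ratio. A separate non-inferiority test on the COV gives 18 subjects, and 22 are to be recruited to allow for 4 drop-outs.

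Section 8.2 sets the test. AUC is analysed on the log scale in a crossover ANOVA: "The terms to be used in the ANOVA model will be sequence, patient within sequence, period, and formulation". The decision rule is "The acceptance range for AUC ratio of the 90% CI for levodopa will be 0.80 to 1.25".

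Section 1.3 reports from the 5 interim patients an LCIG/s.c. bioavailability ratio of 0.78 on AUC0-inf and 0.86 on AUC0-16, and an absolute Duodopa bioavailability of 82% against i.v.

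**The concern.** The sample size should follow from the test that decides the claim. A 90% CI that must lie inside both limits uses z = 1.645 per side. With a true ratio of 1 the type II error is split between the two sides, so 80% power needs z-beta = 1.282. The pair 1.96 and 0.84 belongs to a test for a difference. Power in an equivalence test also depends strongly on the SD of the within-patient difference and on the true ratio, and section 8.1 specifies neither.

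At stake is the planned power of a primary equivalence claim: as written, section 8.1 does not allow a reader to determine it.

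**Working it through.** **Inputs.** From section 8.1: z 1.96 and 0.84; COV 24.5%, 23.8% (17.0 × 1.4) and 17.0%; n = 14, 18 and 22. From section 8.2: limits 0.80 to 1.25, i.e. ±ln 1.25 = ±0.2231, 90% CI, log scale. From section 1.3: interim ratios 0.78 and 82%.

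**1. Reproducing n=14.** Paired difference formula with a 20% difference and a small-sample term of z²/2:

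n = ((1.96 + 0.84) × COV / 20)² + 1.96²/2

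- COV 24.5%: 11.76 + 1.92 = 13.69, rounded up to 14.
- COV 23.8%: 11.10 + 1.92 = 13.02, rounded up to 14.

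Here the COV serves directly as the SD of the test-minus-reference difference. Other forms fail: a 25% difference gives 9.5 and 9.0, ln 1.25 gives 11.4 and 10.8, and treating the COV as within-subject gives 23.5 and 22.2 before any correction. The formula is therefore inferred from fit; the protocol does not print it.

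**2. The constants alone.** TOST at ratio 1 needs 1.645 + 1.282 = 2.93 in place of 2.80, which raises n by a factor (2.93/2.80)² = 1.09. Moving from a margin of 0.20 to 0.2231 lowers it by (0.20/0.2231)² = 0.80. The net effect is a smaller n.

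**3. TOST power of the section 8.2 test.** Power is the probability that |d| < ln 1.25 − t(0.95, df) × s/√n. Here d is normal with mean ln(true ratio) and variance σ²/n, and s² is distributed as σ²χ²/df. The log-scale SD is √ln(1 + COV²), which is 0.2414 for 24.5%. If the COV is the SD of the difference, σ = 0.2414. If it is a within-subject CV, σ = 0.2414 × √2 = 0.3414. Ranges run from df = n−2 (two treatments) to 2n−4 (three treatments).

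True ratio 1.00:

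| COV, reading | n=14 | n=18 | n=22 |
|---|---|---|---|
| 24.5%, SD of difference | 89-91% | 97% | 99% |
| 24.5%, within-subject | 49-54% | 69-72% | 81-83% |
| 17.0%, within-subject | 90-92% | about 97% | 99% |

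With 24.5% at ratio 1, 80% power needs 11-12 subjects on the first reading and 21-22 on the second. At a ratio of 0.95 (my assumption), power at n=14 is 80-82% and 44-47% respectively.

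If 24.5% is instead a COV across subjects, the variance of the difference is 2σ²(1−ρ), where σ² is the log-scale variance across subjects and ρ the correlation between a patient's periods. It equals σ² only when ρ = 0.5.

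**4. The true ratio.** For dose-normalised AUC0-inf, the interim LCIG/s.c. ratio of 0.78 gives s.c./Duodopa = 1/0.78 = 1.28, outside 0.80 to 1.25. With COV 24.5%, power there is about 2-3% at every n from 14 to 23. For i.v., 1/0.82 = 1.22, just inside the limit, and power is about 8-12%. Section 1.3 does not say which AUC the 82% rests on.

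**The case against.** The strongest reply is that the wrong constants do no harm. Step 2 bears this out: under the only COV reading that reproduces n=14, the correct test has about 90% power at ratio 1 and about 80-82% at 0.95. That stands; the z mismatch by itself does not leave n=14 short.

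Second, the low figures need the least favourable reading. If 24.5% is a COV across patients, treating all of it as within-subject error means no correlation between a patient's periods. With the interim 17% as a within-subject CV, power is ample. This also stands: the documents do not settle which reading is right.

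Third, 14 is not the trial size. The COV test sets it at 18, and section 3.1 counts 23 subjects including the interim patients. If those were pooled, power at ratio 1 is 83-85% even on the within-subject reading of 24.5%, although pooling is debatable because the s.c. buffer was changed after the interim (section 1.4). This softens the consequence but does not supply the missing assumptions.

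Fourth, the interim ratios come from 5 patients, before the buffer and bolus rule changed, so they are uncertain. True, but the same interim data were used to set doses and to supply the 17.0%. A power calculation that implicitly takes a ratio of 1 should say why.

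A reader might go further and conclude that the trial is underpowered or bound to fail. The documents do not support either: the COV type is unknown, and the true ratio rests on very few patients. Nor does the protocol name un-normalised AUC as the primary equivalence endpoint. Section 8.1 sizes the dose-normalised AUC0-inf, section 8.2 tests both forms, and the dose-adjusted wording in section 2.1 can be read either way.

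**Conclusion.** The point holds in a limited form. The calculation in section 8.1 belongs to a different test from the one in section 8.2, and n=14 depends on an unstated reading of the COV. The 80% power is implied by z-beta 0.84, not printed. At ratio 1 with COV 24.5% the actual figure at n=14 is either 89-91% or 49-54%, depending on that reading. At n=18 it is 97% or 69-72%.

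For the endpoint that section 8.1 sizes, the sharper problem is the missing true ratio. The protocol's own interim figure for s.c. lies outside the acceptance range, where power is about 2-3% with COV 24.5% at any planned n. A power deficit at a ratio near 1 is not demonstrated. These results assume log-normal AUC, complete data and the interim ratios taken at face value.

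**What to change.** Replace the equivalence paragraph of section 8.1 with a log-scale TOST calculation (one-sided 5% twice, limits 0.80 to 1.25) at n=18. It should:

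- name the endpoint being powered, dose-normalised or un-normalised, and which AUC;
- use the within-subject CV from the interim ANOVA and say that this is what it is;
- state a true ratio consistent with the interim data for that endpoint: about 1.28 s.c./Duodopa for dose-normalised AUC0-inf, or the ratio expected after dose adjustment if un-normalised AUC is the equivalence endpoint;
- report the resulting power, with a range of ratios given how few patients the interim estimate rests on.

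Enrolment need not change. The cost is one rewritten paragraph using interim data already held by the sponsor. The stated power may come out less favourable.
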